14.3.3.4 GAIS Responder Rates

Table 14.3.3.4.1 GAIS Responder Rates (Investigator)

GAIS Respond	er Rate	PraB 40	PraB 20	OnaB 20		P-value	
Investigator		$(\mathbf{n} = \mathbf{x}\mathbf{x})$	$(\mathbf{n} = \mathbf{x}\mathbf{x})$	$(\mathbf{n} = \mathbf{x}\mathbf{x})$	PraB-40 vs. PraB-20	PraB-40 vs. OnaB-20	PraB-20 vs. OnaB-20
V3 (48hrs)	N	XX	XX	XX			
Score 2 or 1	Percent, CI 95%	xx.x% [xx.x, xx.x]	xx.x% [xx.x, xx.x]	xx.x% [$xx.x$, $xx.x$]	X.XXXX	X.XXXX	X.XXXX
	OR (95% CI)				x.xxxx (xx.x, xx.x)	x.xxxx(xx.x, xx.x)	x.xxxx (xx.x, xx.x)
	OR (p-value)				X.XXXX	X.XXXX	X.XXXX
V5 (D30)	N	XX	XX	XX			
Score 2 or 1	Percent, CI 95%	xx.x% [$xx.x$, $xx.x$]	xx.x% [$xx.x$, $xx.x$]	xx.x% [$xx.x$, $xx.x$]	X.XXXX	X.XXXX	X.XXXX
	OR (95% CI)				x.xxxx (xx.x, xx.x)	x.xxxx(xx.x, xx.x)	x.xxxx(xx.x, xx.x)
	OR (p-value)				X.XXXX	X.XXXX	X.XXXX
	N	XX	XX	XX			
Score 2 or 1	Percent, CI 95%	xx.x% [$xx.x$, $xx.x$]	xx.x% [$xx.x$, $xx.x$]	xx.x% [$xx.x$, $xx.x$]	X.XXXX	X.XXXX	X.XXXX
	OR (95% CI)				x.xxxx (xx.x, xx.x)	x.xxxx(xx.x, xx.x)	x.xxxx(xx.x, xx.x)
	OR (p-value)				X.XXXX	X.XXXX	X.XXXX

95% CI [xx.x,xx.x]

<< Insert graph>>

Table 14.3.3.4.2 GAIS Responder Rates (Subject)

GAIS Respond	ler Rate	PraB 40	PraB 20	OnaB 20		P-value	
Subject		$(\mathbf{n} = \mathbf{x}\mathbf{x})$	(n = xx)	(n = xx)	PraB-40 vs. PraB-20	PraB-40 vs. OnaB-20	PraB-20 vs. OnaB-20
V3 (48hrs)	N	XX	XX	XX			
Score 2 or 1	Percent, CI 95%	xx.x% [xx.x, xx.x]	xx.x% [xx.x, xx.x]	xx.x% [$xx.x$, $xx.x$]	X.XXXX	X.XXXX	X.XXXX
	OR (95% CI)				x.xxxx (xx.x, xx.x)	x.xxxx(xx.x, xx.x)	x.xxxx (xx.x, xx.x)
	OR (p-value)				X.XXXX	X.XXXX	X.XXXX
V5 (D30)	N	XX	XX	XX			
Score 2 or 1	Percent, CI 95%	xx.x% [xx.x, xx.x]	xx.x% [xx.x, xx.x]	xx.x% [$xx.x$, $xx.x$]	X.XXXX	X.XXXX	X.XXXX
	OR (95% CI)				x.xxxx (xx.x, xx.x)	x.xxxx(xx.x, xx.x)	x.xxxx (xx.x, xx.x)
	OR (p-value)				X.XXXX	X.XXXX	X.XXXX
	N	XX	XX	XX			
Score 2 or 1	Percent, CI 95%	xx.x% [xx.x, xx.x]	xx.x% [xx.x, xx.x]	xx.x% [$xx.x$, $xx.x$]	X.XXXX	X.XXXX	X.XXXX
	OR (95% CI)				x.xxxx (xx.x, xx.x)	x.xxxx(xx.x, xx.x)	x.xxxx(xx.x, xx.x)
	OR (p-value)				X.XXXX	X.XXXX	X.XXXX

95% CI [xx.x,xx.x]

Confidential Page 49/58

14.3.3.5 SSS Responder Rates

Table 14.3.3.5.1 SSS Responder Rates (Subject)

SSS Responder	r Rate	PraB 40	PraB 20	OnaB 20	Duo D. 40 v.o. Duo D. 20	P-value PraB-40 vs. OnaB-20	PraB-20 vs. OnaB-20
Subject		$(\mathbf{n} = \mathbf{x}\mathbf{x})$	$(\mathbf{n} = \mathbf{x}\mathbf{x})$	$(\mathbf{n} = \mathbf{x}\mathbf{x})$	PraB-40 vs. PraB-20	PraB-40 vs. OnaB-20	PraB-20 vs. OnaB-20
V3 (48hrs)	N	XX	XX	XX			
Score 2 or 1	Percent, CI 95%	xx.x% [$xx.x$, $xx.x$]	xx.x% [$xx.x$, $xx.x$]	xx.x% [$xx.x$, $xx.x$]	X.XXXX	X.XXXX	X.XXXX
	OR (95% CI)				x.xxxx (xx.x, xx.x)	x.xxxx(xx.x, xx.x)	x.xxxx (xx.x, xx.x)
	OR (p-value)				X.XXXX	X.XXXX	X.XXXX
V5 (D30)	N	XX	XX	XX			
Score 2 or 1	Percent, CI 95%	xx.x% [xx.x, xx.x]	xx.x% [xx.x, xx.x]	xx.x% [xx.x, xx.x]	X.XXXX	X.XXXX	X.XXXX
	OR (95% CI)				x.xxxx (xx.x, xx.x)	x.xxxx(xx.x, xx.x)	x.xxxx (xx.x, xx.x)
	OR (p-value)				X.XXXX	X.XXXX	X.XXXX
	N	XX	XX	XX			
Score 2 or 1	Percent, CI 95%	xx.x% [xx.x, xx.x]	xx.x% [xx.x, xx.x]	xx.x% [xx.x, xx.x]	X.XXXX	X.XXXX	X.XXXX
	OR (95% CI)		_		x.xxxx (xx.x, xx.x)	x.xxxx(xx.x, xx.x)	x.xxxx (xx.x, xx.x)
	OR (p-value)				X.XXXX	X.XXXX	X.XXXX

95% CI [xx.x,xx.x]

<< Insert graph>>

14.3.3.6 Onset of Effect

Table 14.3.3.6.1 Onset of Effect (Subject)

Onset of Effect (Days)		$ \begin{array}{l} \text{PraB 40} \\ \text{(n = xx)} \end{array} $	PraB 20 (n = xx)	OnaB 20 (n = xx)	PraB-40 vs. PraB-20	P-value PraB-40 vs. OnaB-20	PraB-20 vs. OnaB-20
Onset	N	XX	XX	XX			
	Days, CI 95%	$x.x \pm x.x [xx.x, xx.x]$	$x.x \pm x.x [xx.x, xx.x]$	$x.x \pm x.x [xx.x, xx.x]$	X.XXXX	X.XXXX	x.xxxx
	OR (95% CI)				x.xxxx (xx.x, xx.x)	x.xxxx (xx.x, xx.x)	x.xxxx (xx.x, xx.x)
	OR (p-value)				X.XXXX	X.XXXX	X.XXXX

95% CI [xx.x,xx.x]

Based on 7-day subject diary

<< Insert graph>>

Confidential Page 50/58

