5.1.4. Clinical Interview (Day 30, Final Visit/Early Termination, and Unscheduled Visit)

Subject opinion regarding study treatment will be assessed through a clinical interview employing the following questions:

- What did you like about the treatment (clinically or other feedback)?
- What did you dislike about the treatment (clinically or other feedback)?
- If treated with botulinum toxin before this study, which treatment did you prefer, the study treatment or the previous treatment?

Version 1.1 31-May-2023 Confidential Page 13/58

5.1.5. 7-Day Subject Diary

In the morning of the day after study treatment, subjects will be issued a 7-day electronic subject diary that will assess subjects' opinion regarding onset of study treatment effect. Subjects will respond "Yes" or "No" to the following question: "Since being injected, have you noticed any effect on the appearance of your glabellar lines?"

Version 1.1 31-May-2023 Confidential Page 14/58

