7.3. Exploratory Effectiveness Endpoints

Exploratory effectiveness endpoints will be evaluated for signals of effectiveness to explore whether any should be elevated in importance for subsequent trials. These endpoints will be assessed using either logistic regression (for binary endpoints) or survival analysis-type methods as described above. Comparisons will be made between all treatment groups. Chi-square tests of association or Fisher's exact tests will be used to compare treatment group differences in proportion of subjects returning to Baseline at each time point in the study. Exploratory endpoints will be:

Version 1.1 31-May-2023 Confidential Page 18/58

- 1. Duration of effect for GLS responders, defined as the number of days from Treatment Day (Baseline) to the day that GLS severity at maximum frown returns to the Baseline value. Analyses will be conducted for Investigator and subject assessments of GLS. Various responder definitions will be tested (1-Point, 2-Point and 3-Point responders at any time during the study; GLS Score of 0 or 1 at any time during the study; 1-Point responders at Day 30).
- 2. Time to loss of GLS responder status, with responder being defined as a GLS score of 0 or 1 at any point during the study. Analyses will be conducted for Investigator and subject assessments of GLS.
- 3. GLS responder rates (Investigator assessments) at each study visit. Various responder definitions will be tested (1-Point, 2-Point and 3-Point responders; GLS Score of 0 or 1; GLS Score 0 or 1 & ≥2-Point improvement; GLS Score 0 or 1 & ≥2-Point improvement & Investigator GLS = subject GLS).
- 4. GLS responder rates (Subject assessments) at each study visit. Various responder definitions will be tested (1-Point, 2-Point and 3-Point responders; GLS Score of 0 or 1).
- 5. GAIS response (score of 2 or 1) as assessed by Investigator and subject at each visit.
- 6. SSS response (score of 2 or 1) as assessed by subjects at each visit.
- 7. Onset of effect as assessed by subjects through the 7-Day Subject Diary.

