7.6. Sample Size Considerations

This study is not powered for inferential analyses. Approximately 150 subjects will be randomized to the study, 50 subjects in each of the three treatment arms; 20U onabotulinumtoxinA, 20U prabotulinumtoxinA and 40U prabotulinumtoxinA. Assuming 50 subjects per treatment group, exponential distributions for failure and censoring times, a median duration of effect of 4 months in the reference group, and an annual censoring rate of 10%, the study will have 80% power to detect a hazard ratio of 0.47 based on a one-sided hypothesis test of the primary effectiveness endpoint with alpha = 0.025. As such, it is the opinion of the study Sponsor that 50 subjects per group (total sample size n=150) will be sufficient to address the objectives of this study.

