7.7. General Considerations

Data will be listed by subject number. Data will be summarized by treatment and study visit, where applicable. For categorical parameters, the number and percentage of subjects/observations in each category will be presented; percentages will be based on the number of subjects in the relevant analysis population in each treatment group. For continuous parameters, descriptive statistics will include n (number of subjects or observations), mean, standard deviation, median, and range. A full description of the statistical methods planned for this study will be provided in the Statistical Analysis Plan (SAP). All programs for data output and analyses will be written in SAS version 9.4 or higher (SAS Institute, Inc., Cary, NC).

Missing Values: For the mITT analysis of primary, secondary, tertiary, and exploratory duration of effectiveness endpoints, in the case of a missed visit, subjects will be considered to have returned to Baseline if they are confirmed to have returned to Baseline at the next non-missed visit. Subjects will be considered to have to have returned to Baseline if they fail to attend 2 consecutive visits or drop out of the study. For missing observations for exploratory endpoints other than duration of effect data will be analyzed as observed without imputation.

Discontinuation and Drop-Outs: Dropouts will not be replaced. Subject disposition will summarize the number of subjects who were randomized and who discontinued from the study (including reasons for discontinuation).

Interim Analysis: An interim analysis will be conducted when >90% of subjects have completed Visit 8 (Day 120) to evaluate response to exposure (efficacy, duration) and adverse events. For assessment of the primary effectiveness endpoint, 95% CIs will be presented but statistical analyses will not be conducted and a statistical penalty for the final analysis will not be employed. While data by treatment group will be presented, individual subjects will not be unblinded.

Poolability of Investigative Sites: Data from all investigative sites will be pooled based on the assumption of clinical comparability: the same protocol will be used for all sites, all sites will be monitored for protocol compliance, and the same data collection instrument and methodology will be used across all sites.

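### The onset table (SAP 14.3.3.6.1) reports days with an odds ratio whose event is not named, and has no rule for subjects without onset by Day 7, so the arm comparison can be biased.

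*SAP*

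**What the plan says.** SAP 5.1.5 (7-Day Subject Diary) provides that "subjects will be issued a 7-day electronic subject diary that will assess subjects' opinion regarding onset of study treatment effect". The subject answers Yes or No to whether any effect has been noticed since injection. Protocol 10.3.6 has the same text.

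SAP 7.3 lists "Onset of effect as assessed by subjects through the 7-Day Subject Diary" as the last of seven exploratory endpoints. For the exploratory set as a whole it states: "These endpoints will be assessed using either logistic regression (for binary endpoints) or survival analysis-type methods as described above". It does not say which method applies to onset.

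The shell for Table 14.3.3.6.1 has the row group "Onset of Effect (Days", footnoted "Based on 7-day subject diary". For each arm it shows one N and a days figure in the form x.x ± x.x with a 95% CI. For the three pairwise comparisons it shows a p-value, then an odds ratio with 95% CI and its own p-value. There is no row for subjects without onset, no censored count, no percent and no hazard ratio.

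The only missing-data text that reaches this endpoint is in SAP 7.7: "For missing observations for exploratory endpoints other than duration of effect data will be analyzed as observed without imputation".

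**The concern.** A subject who answers No on every diary day has no onset day. All that is known is that onset had not been noticed by the last entry, which is right-censoring. Such a subject can enter a mean of days only if a value is assigned, and the SAP assigns none. If the table is filled from subjects who have an onset day, each arm's mean describes a subset selected on the outcome. An arm with slower onset loses more of its slow subjects.

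The odds-ratio rows add a second problem. An odds ratio needs a binary event, and it sits here under a quantity in days. Two programmers could fill this shell in different ways and both be consistent with the text. What is at stake is an onset comparison that could mislead when candidate endpoints for later trials are chosen.

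**Working it through.** **The SAP's own tables.** In the GLS, GAIS and SSS responder-rate shells, the odds-ratio rows stand under a percent row, where the event is clear. In the duration-of-effect shells, the time outcome carries event and censored counts, Kaplan-Meier quartiles and a hazard ratio. The onset shell uses the odds-ratio layout of the first group for a time outcome of the second kind.

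**Inputs.** The documents give no onset rate, mean, SD or odds ratio, so there is no stated figure to reproduce. From the plan: seven diary days, and "50 subjects in each of the three treatment arms" (SAP 7.6). Assumed: one answer per day on Days 1 to 7, and a constant daily chance p of a first Yes, with q = 1 − p.

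**Formulas.**
- No onset by Day 7: q^7.
- Mean day among subjects with onset by Day 7: 1/p − 7q^7/(1 − q^7).
- Mean restricted to 7 days, all subjects: (1 − q^7)/p. This is what a 7-day diary with censoring can estimate.

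**Results.**

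| p | No onset by Day 7 | Onset-only mean | 7-day restricted mean |
|---|---|---|---|
| 0.25 | 0.133 | 4.00 − 7(0.1335/0.8665) = 2.92 | 0.8665/0.25 = 3.47 |
| 0.40 | 0.028 | 2.50 − 7(0.0280/0.9720) = 2.30 | 0.9720/0.40 = 2.43 |
| 0.20 | 0.210 | 5.00 − 7(0.2097/0.7903) = 3.14 | 0.7903/0.20 = 3.95 |
| 0.50 | 0.008 | 2.00 − 7(0.0078/0.9922) = 1.94 | 0.9922/0.50 = 1.98 |

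- 0.25 versus 0.40: restricted-mean difference 1.04 days, onset-only 0.62. Hidden: 1 − 0.62/1.04, about 40%.
- 0.20 versus 0.50: 1.97 against 1.20 days. Hidden: about 39%.

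**Other assumed rates.** Five more constant-chance pairs, set by the proportion with onset by Day 7 (p = 1 − (1 − F)^(1/7)), show how far the share depends on the assumption:

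| Onset by Day 7 | Onset-only difference | Restricted-mean difference | Hidden |
|---|---|---|---|
| 98% vs 95% | 0.31 | 0.44 | 29% |
| 95% vs 90% | 0.29 | 0.48 | 41% |
| 95% vs 80% | 0.61 | 1.17 | 47% |
| 90% vs 70% | 0.54 | 1.22 | 56% |
| 80% vs 60% | 0.37 | 1.00 | 63% |

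**Direction.** Here the proportion ever reporting onset, F, is set separately from timing among those who do. The restricted mean is F × (onset-only mean) + 7(1 − F).
- Everyone has onset by Day 7, timing differs (p = 0.50 vs 0.30): 0.76 days both ways, no bias.
- Both arms 90%, same timing contrast: onset-only 0.76, restricted 0.9 × 0.76 = 0.68, slightly overstated.
- 95% vs 80%, same timing (p = 0.40): onset-only 0.00. Restricted: (0.80 × 2.30 + 1.40) − (0.95 × 2.30 + 0.35) = 0.71 days.
- 95% with p = 0.40 vs 80% with p = 0.55: the onset-only means are 2.30 and 1.79, so the 80% arm looks 0.51 days faster. The restricted means are 0.95 × 2.30 + 0.35 = 2.53 and 0.80 × 1.79 + 1.40 = 2.83, so it is 0.30 days slower. The sign reverses.

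**Power.** Simulation with 50 per arm, two-sided 0.05, 4,000 runs, constant daily chance, 95% vs 80% onset by Day 7: 36% for a t-test in subjects with onset, 52% for Fisher's exact test on onset by Day 7, 82% for a log-rank test censored at Day 7. The t-test is an assumption, because the shell does not name its test.

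**The case against.** The strongest reply is that this is under-specification and not a known wrong analysis. Several parts of it stand.

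- A reader might infer that the SAP excludes subjects without onset. It does not say so. The days row is not labelled as a mean, N is undefined, and the as-observed rule covers missing observations, whereas seven recorded No answers are not missing. The point is only that a mean of days cannot hold these subjects without an assigned value, and none is given.
- SAP 7.3 permits survival-type methods. That is correct, but the text does not assign them to onset and the shell shows none of their output.
- The odds ratio need not be meaningless. Onset by Day 7, yes or no, is a natural event for the logistic regression named in 7.3, and it would keep every subject with a complete diary. At 95% versus 80% it would be (0.95/0.05)/(0.80/0.20) = 4.75. The fault is that the event is not named.
- A reader might infer that the table must understate a difference. The cases above show no bias, slight overstatement and reversal as well.
- A reader might compare with the untruncated means 1/p, 4.0 and 2.5 days for 0.25 versus 0.40, and conclude that more than half of a 1.5-day difference is lost. A 7-day diary cannot estimate those means without a distributional assumption. Against the estimable benchmark, that pair loses about 40%.
- Onset is the last exploratory endpoint in a study that the SAP says is not powered for inference. That limits the importance of the point. It does not supply the missing rule.

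**Conclusion.** The point holds as a defect of the table shell and its missing rule. Filled as laid out, the table gives a days comparison that can be biased, most often toward no difference, and an odds ratio that cannot be interpreted until its event is named.

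The size rests wholly on assumed onset rates: about 40% of the restricted-mean difference is hidden for the two main pairs, and 29% to 63% across all seven constant-chance pairs. The bias vanishes if every subject reports onset by Day 7. The direction is not guaranteed, and the documents do not show that subjects without onset will be dropped. No primary or secondary conclusion depends on this table, so the change is worth making but not critical.

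**What to change.** In Table 14.3.3.6.1, replace the days row with time from treatment to first Yes, censored at the last completed diary day. Show the numbers with onset and censored, Kaplan-Meier estimates, and a Cox hazard ratio with 95% CI. State how ties are handled, since there are only seven possible days. Add a row for the percent with onset by Day 7. Then either define the odds ratio as onset by Day 7 (yes/no) and place it under that percent, or delete it.

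In SAP 7.3, add one sentence that defines the onset day, names the method for this endpoint and states the censoring rule, including for a subject who answers No throughout.

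The cost is one table shell and one sentence. No new data are needed, and the methods are already permitted by SAP 7.3.

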14.4 Safety Data

14.4.1 Adverse Events

Table 14.4.1.1 Adverse Event Profile Overview

		PraB 40	PraB 20	OnaB 20
Adverse Events – All Subjects		$(\mathbf{n} = \mathbf{x}\mathbf{x})$	$(\mathbf{n} = \mathbf{x}\mathbf{x})$	$(\mathbf{n} = \mathbf{x}\mathbf{x})$
Participants with any TEAE ^a	Participants	xx (xx.x%) [xx.x, xx.x]	xx (xx.x%) [xx.x, xx.x]	xx (xx.x%) [xx.x, xx.x]
	Events	XXX	XXX	XXX
	Events/Participants	XXX	XXX	XXX
Participants with any TRAE ^b	Participants	xx (xx.x%) [xx.x, xx.x]	xx (xx.x%) [xx.x, xx.x]	xx (xx.x%) [xx.x, xx.x]
	Events	XXX	XXX	XXX
	Events/Participants	XXX	XXX	XXX
Participants with SAE ^c	Participants	xx (xx.x%) [xx.x, xx.x]	xx (xx.x%) [xx.x, xx.x]	xx (xx.x%) [xx.x, xx.x]
	Events	XXX	XXX	XXX
	Events/Participants	XXX	XXX	XXX
Participants with any TRSAE ^d	Participants	x (xx.x%) [xx.x, xx.x]	xx (xx.x%) [xx.x, xx.x]	xx (xx.x%) [xx.x, xx.x]
	Events	XXX	XXX	XXX
	Events/Participants	XXX	XXX	XXX
Participants with UADRe	Participants	xx (xx.x%) [xx.x, xx.x]	xx (xx.x%) [xx.x, xx.x]	xx (xx.x%) [xx.x, xx.x]
	Events	XXX	XXX	XXX
	Events/Participants	XXX	XXX	XXX
Participants with AESIf	Participants	xx (xx.x%) [xx.x, xx.x]	xx (xx.x%) [xx.x, xx.x]	xx (xx.x%) [xx.x, xx.x]
	Events	xxx	XXX	XXX
	Events/Participants	XXX	XXX	XXX

95% CI [xx.x, xx.x]. aTEAE= Treatment-Emergent AE. bTRAE= Treatment-Related AE. cVADR= Unexpected Adverse Drug Reaction. AESI= Adverse Effect of Special Interest. Number of Participants (% in parenthesis).

Confidential Page 51/58

Table 14.4.1.2 Treatment-Emergent Adverse Events Sorted by SOC and PT

		PraB 40 (n = xx)		PraB 20 (n = xx)		OnaB 20 (n = xx)	
SOC	PT	Participants	Events	Participants	Events	Participants	Events
Any TEAE		xx (xx.x%) [xx.x, xx.x]	XX	xx (xx.x%) [xx.x, xx.x]	XX	xx (xx.x%) [xx.x, xx.x]	XX
XXXXXXX		xx (xx.x%) [xx.x, xx.x]	XX	xx (xx.x%) [xx.x, xx.x]	XX	xx (xx.x%) [xx.x, xx.x]	XX
	XXXXXXX	xx (xx.x%) [xx.x, xx.x]	XX	xx (xx.x%) [xx.x, xx.x]	XX	xx (xx.x%) [xx.x, xx.x]	XX
XXXXXXX		xx (xx.x%) [xx.x, xx.x]	XX	xx (xx.x%) [xx.x, xx.x]	XX	xx (xx.x%) [xx.x, xx.x]	XX
	XXXXXXX	xx (xx.x%) [xx.x, xx.x]	XX	xx (xx.x%) [xx.x, xx.x]	XX	xx (xx.x%) [xx.x, xx.x]	XX

95% CI [xx.x, xx.x] Number of Participants (% in parenthesis).

Table 14.4.1.3 Treatment-Related Adverse Events Sorted by SOC and PT

		PraB 40 (n = xx)		PraB 20 (n = xx)		OnaB 20 (n = xx)	
SOC	PT	Participants	Events	Participants	Events	Participants	Events
Any TRAE		xx (xx.x%) [xx.x, xx.x]	XX	xx (xx.x%) [xx.x, xx.x]	XX	xx (xx.x%) [xx.x, xx.x]	XX
XXXXXXX		xx (xx.x%) [xx.x, xx.x]	XX	xx (xx.x%) [xx.x, xx.x]	XX	xx (xx.x%) [xx.x, xx.x]	XX
	XXXXXXX	xx (xx.x%) [xx.x, xx.x]	XX	xx (xx.x%) [xx.x, xx.x]	XX	xx (xx.x%) [xx.x, xx.x]	XX
XXXXXXX		xx (xx.x%) [xx.x, xx.x]	XX	xx (xx.x%) [xx.x, xx.x]	XX	xx (xx.x%) [xx.x, xx.x]	XX
	XXXXXXX	xx (xx.x%) [xx.x, xx.x]	XX	xx (xx.x%) [xx.x, xx.x]	XX	xx (xx.x%) [xx.x, xx.x]	XX

95% CI [xx.x, xx.x] Number of Participants (% in parenthesis).

Table 14.4.1.4 Treatment-Emergent Serious Adverse Events Sorted by SOC and PT

		PraB 40		PraB 20		OnaB 20	
		$(\mathbf{n} = \mathbf{x}\mathbf{x})$		$(\mathbf{n} = \mathbf{x}\mathbf{x})$		$(\mathbf{n} = \mathbf{x}\mathbf{x})$	
SOC	PT	Participants	Events	Participants	Events	Participants	Events
Any TESAE		xx (xx.x%) [xx.x, xx.x]	XX	xx (xx.x%) [xx.x, xx.x]	XX	xx (xx.x%) [xx.x, xx.x]	XX
XXXXXXX		xx (xx.x%) [xx.x, xx.x]	XX	xx (xx.x%) [xx.x, xx.x]	XX	xx (xx.x%) [xx.x, xx.x]	XX
	XXXXXXX	xx (xx.x%) [xx.x, xx.x]	XX	xx (xx.x%) [xx.x, xx.x]	XX	xx (xx.x%) [xx.x, xx.x]	XX
XXXXXXX		xx (xx.x%) [xx.x, xx.x]	XX	xx (xx.x%) [xx.x, xx.x]	XX	xx (xx.x%) [xx.x, xx.x]	XX
	XXXXXXX	xx (xx.x%) [xx.x, xx.x]	XX	xx (xx.x%) [xx.x, xx.x]	XX	xx(xx.x%)[xx.x,xx.x]	XX

95% CI [xx.x, xx.x] Number of Participants (% in parenthesis).

Version 1.1 31-May-2023 Confidential Page 52/58

Table 14.4.1.5 Treatment-Related Serious Adverse Events Sorted by SOC and PT

•	•	PraB 40		PraB 20	•	OnaB 20	
		$(\mathbf{n} = \mathbf{x}\mathbf{x})$		$(\mathbf{n} = \mathbf{x}\mathbf{x})$		$(\mathbf{n} = \mathbf{x}\mathbf{x})$	
SOC	PT	Participants	Events	Participants	Events	Participants	Events
Any TRSAE		xx (xx.x%) [xx.x, xx.x]	XX	xx (xx.x%) [xx.x, xx.x]	XX	xx (xx.x%) [xx.x, xx.x]	XX
XXXXXXX		xx (xx.x%) [xx.x, xx.x]	XX	xx (xx.x%) [xx.x, xx.x]	XX	xx (xx.x%) [xx.x, xx.x]	XX
	XXXXXXX	xx (xx.x%) [xx.x, xx.x]	XX	xx (xx.x%) [xx.x, xx.x]	XX	xx (xx.x%) [xx.x, xx.x]	XX
XXXXXXX		xx (xx.x%) [xx.x, xx.x]	XX	xx (xx.x%) [xx.x, xx.x]	XX	xx (xx.x%) [xx.x, xx.x]	XX
	XXXXXXX	xx (xx.x%) [xx.x, xx.x]	XX	xx (xx.x%) [xx.x, xx.x]	XX	xx(xx.x%)[xx.x,xx.x]	XX

95% CI [xx.x, xx.x] Number of Participants (% in parenthesis).

Table 14.4.1.6 Unexpected Adverse Drug Reactions Sorted by SOC and PT

		PraB 40 (n = xx)	PraB 40 (n = xx)			OnaB 20 (n = xx)	
SOC	PT	Participants	Events	Participants	Events	Participants	Events
Any UADR		xx (xx.x%) [xx.x, xx.x]	XX	xx (xx.x%) [xx.x, xx.x]	XX	xx (xx.x%) [xx.x, xx.x]	XX
XXXXXXX		xx (xx.x%) [xx.x, xx.x]	XX	xx (xx.x%) [xx.x, xx.x]	XX	xx (xx.x%) [xx.x, xx.x]	XX
	XXXXXXX	xx (xx.x%) [xx.x, xx.x]	XX	xx (xx.x%) [xx.x, xx.x]	XX	xx (xx.x%) [xx.x, xx.x]	XX
XXXXXXX		xx (xx.x%) [xx.x, xx.x]	XX	xx (xx.x%) [xx.x, xx.x]	XX	xx (xx.x%) [xx.x, xx.x]	XX
	XXXXXXX	xx(xx.x%)[xx.x,xx.x]	XX	xx (xx.x%) [xx.x, xx.x]	XX	xx(xx.x%)[xx.x,xx.x]	XX

95% CI [xx.x, xx.x] Number of Participants (% in parenthesis).

Table 14.4.1.7 Adverse Events of Special Interest Sorted by SOC and PT

		PraB 40 (n = xx)		PraB 20 (n = xx)		OnaB 20 (n = xx)	
SOC	PT	Participants	Events	Participants	Events	Participants	Events
Any AESI		xx (xx.x%) [xx.x, xx.x]	XX	xx (xx.x%) [xx.x, xx.x]	XX	xx (xx.x%) [xx.x, xx.x]	XX
XXXXXXX		xx (xx.x%) [xx.x, xx.x]	XX	xx (xx.x%) [xx.x, xx.x]	XX	xx (xx.x%) [xx.x, xx.x]	XX
	XXXXXXX	xx (xx.x%) [xx.x, xx.x]	XX	xx (xx.x%) [xx.x, xx.x]	XX	xx (xx.x%) [xx.x, xx.x]	XX
XXXXXXX		xx (xx.x%) [xx.x, xx.x]	XX	xx (xx.x%) [xx.x, xx.x]	XX	xx (xx.x%) [xx.x, xx.x]	XX
	XXXXXXX	xx (xx.x%) [xx.x, xx.x]	XX	xx (xx.x%) [xx.x, xx.x]	XX	xx (xx.x%) [xx.x, xx.x]	XX

95% CI [xx.x, xx.x] Number of Participants (% in parenthesis).

Confidential Page 53/58

